7.8.4 CLINICAL TRIAL STOPPING RULES

The Investigator is to immediately notify the Medical Monitor if the following are observed:

- Any SAE related to study treatment;
- Any Grade 4 AEs related to study treatment;
- Any report of anaphylaxis related to study treatment;
- Any suspected Severe COVID-19 disease case (per Sections 3.7.1.1 and Section 3.7.1.2).

The Medical Monitor will notify the Chair of the Safety Review Committee, who will make a determination as to whether to temporarily halt dosing until a more formal review of the case(s) is made. Such a formal review may include an ad hoc meeting of the DSMB, after consultation with the DSMB Chair. Following such a meeting, the DSMB chair will render a recommendation to the Medical Monitor regarding continuation of trial dosing. The Sponsor will independently investigate the case(s) and, after review of the DSMB recommendations, will communicate a final decision as to whether to lift the dosing suspension or whether to continue dosing. These deliberations will be documented and will be provided to the IRBs and FDA, where required.

In the case of suspected Severe COVID-19 cases, the trial will be paused if a vaccine-toplacebo case split yields a relative risk with a 90% confidence interval lower bound >1. The minimum case split corresponding to this criterion is 8:0. In this scenario, the trial will pause until at least one additional case is accrued and the DSMB can review the data and make a recommendation regarding continued enrollment in the trial.

7.10 ADVERSE EVENT REPORTING

This section provides details on reporting the safety information.

7.10.1 SUBMITTING THE INITIAL SERIOUS ADVERSE EVENT (SAE) REPORT FORM

The Investigator should include as much safety information as possible when submitting the initial report, but the report must include the following at a minimum:

• The adverse event;

INO-4800	COVID19-311
Inovio Pharmaceuticals, Inc.	Clinical Protocol

- The subject's assigned identification number (SID);
- Investigational product(s) (IP) and/or study device;
- Investigator causal relationship to the IP(s) and/or study device;
- Serious criteria;
- Reporter name and contact information.

If a case is submitted to the Sponsor with only the "minimum" information, a more detailed or updated follow-up report will be sent to the Sponsor as soon as possible but no later than three (3) calendar days after the date of the initial report.

7.10.2 **Recording the Event**

Investigators should use correct medical terminology/concepts when recording AEs on the EDC and SAE Report Form. The use of colloquialisms and abbreviations should be avoided.

A medical diagnosis, if known, should be recorded rather than individual signs and symptoms. However, if the signs and/or symptoms cannot be medically characterized as a single diagnosis or syndrome, each individual sign and/or symptom should be recorded. If a diagnosis is subsequently established, all previous signs and/or symptoms will be subsumed and replaced with a single medical diagnosis.

7.10.3 Assessing Severity (Intensity)

Severity is used to describe the intensity of a specific event (e.g., mild, moderate, severe).

The Investigator will assess and grade clinical AEs or SAEs (based on discussions with clinical trial subjects) in accordance with CTCAE.

7.10.4 CAUSAL RELATIONSHIP OF CLINICAL MATERIAL TO ADVERSE EVENTS (AES)

A causally related AE is one judged to have a possible, probable or definite relationship to the administration of the IP and/or the study device. An AE may also be assessed as not related to the IP and/or the study device. Because the Investigator is knowledgeable about the subject (e.g., medical history, concomitant medications), administers the IP, and monitors the subject's response to the IP, the Investigator is responsible for reporting AEs and judging the relationship between the administration of the IP and EP and a subsequent AE. The Investigator is aware of the subject's clinical state and may have observed the event, and thus may be sensitive to distinctions between events due to the underlying disease process versus events that may be product-related.

Investigators should use their knowledge of the clinical trial subject, the circumstances surrounding the event, and an evaluation of any potential alternative causes to determine whether an AE is considered to be related to the IP and/or the study device and the causal relationship reported as "Yes" or "No" accordingly. Causality should be assessed by the Investigator as related to drug, related to device, or related to both drug and device (i.e., related to both or indiscernible) by the following criteria:

- Yes there is a reasonable possibility that administration of the clinical trial treatment (drug or device or both drug and device) contributed to the event
- No there is no reasonable possibility that administration of the clinical trial treatment contributed to the event and there are more likely causes

INO-4800	COVID19-311
Inovio Pharmaceuticals, Inc.	Clinical Protocol

The following guidance should also be taken into consideration:

- Temporal relationship of event to administration of IP and/or EP;
- Course of the event, considering especially the effects of dose reduction, discontinuation of IP, or reintroduction of IP (where applicable);
- Known association of the event with the IP, EP or with similar treatments;
- Known association of the event with the disease under trial;
- Presence of risk factors in the clinical trial subject or use of concomitant medications known to increase the occurrence of the event.

The rationale for the Investigator's causal assessment is to be recorded on the SAE Report Form.

The Sponsor will assess the overall safety of the IP delivered by EP and determine whether to report expeditiously to the regulatory authority(ies).

7.11 REPORTING SUSPECTED COVID-19 DISEASE CASES DURING THE TRIAL

For both Phase 2 and Phase 3 segments of the trial, all suspected COVID-19 disease cases based on reported COVID-19 symptoms and/or SARS-CoV-2 test results should be entered into the Suspected COVID-19 Clinical Event CRF within 24 hours of awareness. Cases will be tracked until final determination of whether the case meets criteria of a confirmed COVID-19 disease case, per the case definition. For the Phase 2 segment of the trial, this determination will be made by the Investigator. For the Phase 3 segment, this determination will be made by the EAC.

If the reported COVID-19 disease case is later determined not to be a confirmed COVID-19 case, the event (e.g. symptoms or other diagnosis), if serious, would be reported as an SAE within 24 hours following determination by the Investigator (Phase 2 segment) or notification by EAC (Phase 3 segment).

If the reported COVID-19 disease case is later determined not to be a confirmed COVID-19 case, the event (e.g. symptoms or other diagnosis), if non-serious and if occurring from the time of consent until 28 days post-dose 2, would be reported as an AE following determination by the Investigator (Phase 2 segment) or notification by EAC (Phase 3 segment).

7.12 **REPORTING PREGNANCY DURING THE CLINICAL TRIAL**

Subjects in Phase 2 who are pregnant or expect to become pregnant prior to 3 months following the last dose will be excluded from participation in the clinical trial.

Subjects in Phase 3 who are pregnant or expect to become pregnant prior to the last dose will be excluded from participation in the clinical trial.

All pregnancies that occur from the time of first administration of clinical trial treatment through study completion (i.e., Day 393) will be reported to the Sponsor. If clinical trial site staff become aware that a subject becomes pregnant after the first dose in the clinical trial, she will not be given any additional treatments with the IP. A Pregnancy Form will be completed by the site and submitted to the Sponsor within 24 hours after becoming aware of the pregnancy.

The Investigator will report this event to their IRB/REB/EC in accordance with their policies and procedures.

INO-4800	COVID19-311
Inovio Pharmaceuticals, Inc.	Clinical Protocol

The clinical trial site must request the subject's permission to query pregnancy outcome and follow the subject for outcome of the pregnancy. The subject will continue to be followed for safety assessments without receiving additional IP until clinical trial discharge in accordance with this protocol. Procedures that are contraindicated during pregnancy, including additional dose administrations, must not be performed. The Investigator should use clinical judgment regarding subsequent clinical trial-related blood collection based on the presence or absence of anemia in each subject.

Male subjects will be instructed through the ICF to immediately inform the Investigator if their partner becomes pregnant until study completion. A Pregnancy Form will be completed by the site and submitted to the Sponsor within 24 hours after becoming aware of the pregnancy. The pregnant partner will be asked to sign a Pregnancy Information Collection Consent Form to allow for follow-up on her pregnancy. If the authorization has been signed, the Investigator will collect and report details of the course and outcome of the pregnancy in the partner of a male subject exposed to IP. The site will update the Pregnancy Form with additional information on the course and outcome of the pregnancy and submit the form to the Sponsor.

If an Investigator is contacted by the male subject or his pregnant partner, the Investigator may provide information on the risks of the pregnancy and the possible effects on the fetus to support an informed decision in cooperation with the treating physician and/or obstetrician.

If the end of the pregnancy occurs after the clinical trial has been completed, the outcome will be reported directly to the Sponsor.

7.13 **REPORTING DEVICE-RELATED COMPLAINTS OR DEFICIENCIES**

All product complaints that meet the definition of device deficiency must be reported to the Sponsor within 10 days of discovery, with the exception of SAEs which require 24-hour reporting. The error reporting or complaint form must be completed and emailed to the Sponsor at [contact].

Device deficiencies include malfunctions, misuse or use errors and inadequate labeling. A malfunction is defined as the failure of a device to meet its performance specifications or otherwise perform as intended. The intended performance of a device refers to the intended use for which the device is labeled or marketed.

Any problems experienced during the treatment procedure including malfunctions of the device, error messages displayed on the device screen following treatment, or errors that occur during the treatment procedure must immediately be reported to the Sponsor or its designee for evaluation.

7.14 NOTIFYING REGULATORY AUTHORITIES AND INSTITUTIONAL REVIEW BOARDS (IRBS)/RESEARCH ETHICS BOARDS (REBS)/ETHICS COMMITTEES (ECS) OF SAFETY INFORMATION

7.14.1 SPONSOR RESPONSIBILITIES

- Determine whether the safety information meets the requirements for expedited reporting to the applicable regulatory authorities;
- Prepare and submit the safety report to the applicable regulatory authorities;
- Send all participating PIs a safety report and Investigator Safety Letter (i.e., Dear Investigator Letter) that will include a statement if there is or is not any significant new safety information that might influence the risk-benefit assessment of the IP and/or

INO-4800	COVID19-311
Inovio Pharmaceuticals, Inc.	Clinical Protocol

study device, sufficient to consider changes in product administration or overall conduct of the clinical investigation.

7.14.2 PRINCIPAL INVESTIGATOR (PI) RESPONSIBILITIES

- Forward a copy of the safety report and Investigator Safety Letter (i.e., Dear Investigator Letter) to their IRB/REB/EC as soon as practical in accordance with the governing policy and/or procedures;
- Notify their IRB/REB/EC of safety information (i.e., SAEs, pregnancies, and AESIs) that occur at their clinical trial site in accordance with their local institutional policy.

7.15 **POST-TRIAL REPORTING REQUIREMENTS**

PIs are not obligated to actively seek AEs or SAEs beyond the clinical trial reporting period. However, if the PI becomes aware of an AE or SAE that occurs after the Completion or Termination Visit and the event is deemed by the PI to be related to the clinical trial treatment, the PI should promptly document and report the event to the Sponsor.

7.16 CLINICAL TRIAL DISCONTINUATION

INOVIO reserves the right to discontinue the clinical trial at a site or at multiple sites for safety or administrative reasons at any time. In particular, a clinical trial site that does not recruit at a reasonable rate may be discontinued. Additionally, the clinical trial may be discontinued at any time by an IRB/REB/EC, INOVIO, or a regulatory authority as part of their duties to ensure that clinical trial subjects are protected.

If the clinical trial is discontinued and/or the clinical trial site closed for any reason, all IP and devices must be returned to INOVIO or its representative. The PI should ensure that their site file documents are complete prior to archiving, and provide copies of any requested documents to INOVIO for its Trial Master File (TMF).

8.0 **STATISTICAL CONSIDERATIONS**

8.1 STATISTICAL AND ANALYTICAL PLAN

The formal Statistical Analysis Plan is contained in the sections that follow.

8.2 **GENERAL CONSIDERATIONS**

The statistical analysis of the data will be performed by Inovio Pharmaceuticals or its representative.

This is an operationally seamless Phase 2/3 trial. The subjects and data from Phase 2 are independent from that of Phase 3.

Phase 2 Segment: This is a four-arm, multi-center, placebo-controlled, blinded, and randomized clinical trial in subjects at high risk of SARS-CoV-2 exposure. The trial's primary endpoints are antigen-specific cellular immune response measured by IFN-gamma ELISpot and neutralizing antibody responses. Secondary efficacy endpoints are safety measures. Exploratory endpoints are antigen-specific cellular immune response measured by flow cytometry and other T and B cell measures.

Phase 3 Segment: This is a two-arm, multi-center, placebo-controlled, double-blinded, and randomized clinical trial in subjects at high risk of SARS-CoV-2 exposure. The study's

INO-4800	COVID19-311
Inovio Pharmaceuticals, Inc.	Clinical Protocol

primary endpoint is the incidence of virologically-confirmed COVID-19 disease in subjects who are SARS-CoV-2 seronegative at baseline starting 14 days after completion of the 2-dose regimen until 12 months post-dose 2. The primary hypothesis is that INO-4800 will be efficacious relative to placebo (relative efficacy > 30%). Secondary efficacy analyses involve non-severe cases, severe cases, cases resulting in death, and cases among baseline SARS-CoV-2 seropositive subjects. Other secondary analyses concern safety and cellular and neutralizing antibody response. Exploratory analyses concern efficacy against variants, efficacy against asymptomatic infection, and binding antibody and cellular immunological measures.

8.3 **STATISTICAL HYPOTHESES**

Phase 2 Segment: This is an estimation segment pertaining to immunogenicity and safety. There are no hypotheses.

Phase 3 Segment: The primary hypothesis of relative efficacy greater than 30% among baseline SARS-CoV-2 seronegative subjects will be tested with H₀: $p \ge .70/(.70+k)$ vs. H₁: p < .70/(.70+k), where p is the true proportion of subjects with disease who receive INO-4800 relative to the total number of subjects with disease, and k is the total amount of follow-up time in the placebo group divided by the total amount of follow-up time in the INO-4800 group. There are no other formal hypotheses.

8.4 ANALYTICAL POPULATIONS

Analysis populations will be:

The per-protocol (PP) population includes all subjects who receive all doses of Study Treatments and have no protocol violations. Subjects in the PP population will be grouped to treatment arms as randomized. Subjects excluded from the PP population will be identified and documented prior to unblinding of the trial database. Analyses on the PP population among those who are baseline SARS-CoV-2 seronegative will be primary for the analyses of efficacy in the Phase 3 segment of this trial.

The modified intention to treat (mITT) population includes all subjects who receive at least one dose of Study Treatment. Subjects in this population will be grouped to treatment arms as randomized. Analysis of the mITT population will be considered supportive for the corresponding PP population for the analyses of efficacy in the Phase 3 segment of this trial.

The intention to treat (ITT) population includes all subjects who are randomized. Subjects in this sample will be grouped to treatment arms as randomized. Analysis of the ITT population will be considered supportive for the corresponding PP population for the analyses of efficacy in the Phase 3 segment of this trial.

The safety analysis population includes all subjects who receive at least one dose of Study Treatment. Subjects will be analyzed according to the treatments received.

8.5 **DESCRIPTION OF STATISTICAL METHODS**

8.5.1 PRIMARY ANALYSIS

Phase 2 Segment

Post-baseline increases from baseline in interferon-γ ELISpot response magnitudes will be compared between treatment groups using differences in medians and associated non-parametric 95% CIs.

INO-4800	COVID19-311
Inovio Pharmaceuticals, Ind	. Clinical Protocol

Post-baseline increases from baseline in neutralizing antibody response titers will be compared between treatment groups using ratios of geometric mean fold-rises and associated t-distribution based 95% CIs.

The summaries listed above will be stratified according to NP positive/negative status of the subjects. Valid samples for statistical analysis purposes will be those collected: at least 6 and no more than 30 days after Dose 2 for the Week 6 timepoint; at least 174 and no more than 198 days after Dose 2 for the Week 30 timepoint; and at least 356 and no more than 380 days after Dose 2 for the Week 56 timepoint. Baseline is defined as the last measurement prior to the first treatment administration.

The PP population will be used for these immunogenicity analyses.

Phase 3 Segment

Among subjects who are SARS-CoV-2 seronegative at baseline, the primary hypothesis of relative efficacy greater than 30% will be tested with H₀: $p \ge 0.70/(0.70+k)$ vs. H₁: p < 0.70/(0.70+k), where p is the true proportion of subjects with disease who receive INO-4800 relative to the total number of subjects with disease, and k is the total amount of follow-up time in the placebo group divided by the total amount of follow-up time in the INO-4800 group.

A p-value for this hypothesis test and corresponding confidence interval will be computed based on the exact binomial method of Clopper-Pearson. Success will be concluded if the one-sided p-value is <0.022 and the corresponding lower bound of the two-sided 95.6% Cl for efficacy exceeds 30% (alpha-level adjusted for interim analyses, see Section 8.5.6), and the point estimate for efficacy exceeds 50%.

For calculating k, an individual subject's follow-up time is either:

- $\circ~$ the date of first disease diagnosis date of the start of surveillance period +1 (for subjects who are cases), or
- the date of last follow-up date of the start of surveillance period +1 (for subjects who are non-cases).

This methodology is based on the following. Assuming that the number of subjects who are cases in the INO-4800 group follows a Poisson distribution with parameter λ_v and the number of subjects who are cases in the placebo group follows a Poisson distribution with parameter λ_c , then conditional on total number of subjects with cases, t, the number of subjects who are cases in the INO-4800 group follows a binomial distribution with parameters (t, $p = \lambda_v/(\lambda_v + \lambda_c)$). The relationship between p and efficacy is: efficacy = (1-(1+k)p)/(1-p). Therefore, testing efficacy > 30% corresponds to testing p < 0.70/(0.70+k). Similarly, the confidence interval for efficacy is (1-(1+k)UB_p)/(1-UB_p), (1-(1+k)LB_p)/(1-LB_p), where UB and LB are the Clopper-Pearson upper and lower limits for the proportion.

The efficacy time frame is defined by symptoms beginning at any time starting from 14 days after Dose 2 and ending 12 months after Dose 2. Subjects identified as cases that started prior to this time point will be excluded. Subjects with multiple instances meeting the case definition will be counted only once, using the first such instance.

The PP population will be primary for the analysis of efficacy in this trial. Efficacy analysis using the mITT population will also be conducted counting cases from 14 days postdose 1 as a supportive analysis. The ITT population will also be used for a supportive analysis counting cases starting from randomization.

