8.5.2.2 Immunogenicity

Phase 3 Segment

Post-baseline increases from baseline in interferon- γ ELISpot response magnitudes will be compared between treatment groups using differences in medians and associated non-parametric 95% CIs.

Post-baseline increases from baseline in neutralizing antibody response titers will be compared between treatment groups using ratios of geometric mean fold-rises and associated t-distribution based 95% CIs.

The summaries listed above will be stratified according to disease status of the subjects and by baseline SARS-CoV-2 serostatus.

Valid samples for statistical analysis purposes will be those collected: at least 6 and no more than 30 days after Dose 2 for the Week 6 timepoint; at least 174 and no more than 198 days after Dose 2 for the Week 30 timepoint; and at least 356 and no more than 380 days after Dose 2 for the Week 56 timepoint... Baseline is defined as the last measurement prior to the first treatment administration.

The PP population will be used for these immunogenicity analyses.

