8.5.9.2 Immunogenicity

Phase 2 segment

INO-4800	COVID19-311
Inovio Pharmaceuticals, Inc.	Clinical Protocol

Post-baseline increases from baseline in cellular response magnitudes will be compared between treatment groups using differences in medians and associated non-parametric 95% CIs.

The summaries listed above will be stratified according to NP positive/negative status of the subjects.

Valid samples for statistical analysis purposes will be those collected: at least 6 and no more than 30 days after Dose 2 for the Week 6 timepoint; at least 174 and no more than 198 days after Dose 2 for the Week 30 timepoint; and at least 356 and no more than 380 days after Dose 2 for the Week 56 timepoint. Baseline is defined as the last measurement prior to the first treatment administration.

The PP population will be used for immunogenicity analyses.

Phase 3 Segment

Post-baseline increases in antibody titers from ELISA will be compared between treatment groups using ratios of geometric mean fold-rises and associated 95% t-distribution based CIs.

Post-baseline increases from baseline in cellular response magnitudes will be compared between treatment groups using differences in medians and associated non-parametric 95% CIs.

Post-baseline increases from baseline in neutralizing antibody response titers will be compared between treatment groups using ratios of geometric mean fold-rises and associated t-distribution based 95% CIs.

The summaries listed above will be stratified according to disease status of the subjects.

Valid samples for statistical analysis purposes will be those collected: at least 6 and no more than 30 days after Dose 2 for the Week 6 timepoint; at least 174 and no more than 198 days after Dose 2 for the Week 30 timepoint; and at least 356 and no more than 380 days after Dose 2 for the Week 56 timepoint. Baseline is defined as the last measurement prior to the first treatment administration.

The PP population will be used for immunogenicity analyses.

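### The titer comparisons fix the baseline coefficient at 1 and ignore age group and the Phase 3 randomization strata, so their intervals are valid but may be wider than necessary

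*Protocol*

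**What the plan says.** The current text is version 5.0. Section 8.5.1 has the Phase 2 primary neutralizing-antibody titers "compared between treatment groups using ratios of geometric mean fold-rises and associated t-distribution based 95% CIs". Section 8.5.2.2 uses the same method for the Phase 3 secondary analysis. Section 8.5.9.2 uses it again for Phase 3 exploratory neutralizing antibody, and compares ELISA titers by "ratios of geometric mean fold-rises and associated 95% t-distribution based CIs". ELISpot increases are "compared between treatment groups using differences in medians and associated non-parametric 95% CIs".

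None of these passages names a covariate. They do name strata. For Phase 2: "The summaries listed above will be stratified according to NP positive/negative status of the subjects". For the Phase 3 secondary analysis: "The summaries listed above will be stratified according to disease status of the subjects and by baseline SARS-CoV-2 serostatus". The Phase 3 exploratory summaries are stratified by disease status only.

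A baseline value is available: "Baseline is defined as the last measurement prior to the first treatment administration". Age is used elsewhere in the design. It sets the Phase 2 enrolment targets (240, 120 and 40 subjects), it is one of two Phase 3 randomization strata alongside risk condition (Section 8.7), and it is the level at which Section 1.3.7 places the dose decision.

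Section 8.1 states: "The formal Statistical Analysis Plan is contained in the sections that follow". The method is therefore fixed here and not left to another document.

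**The concern.** A ratio of geometric mean fold-rises is, on the log scale, a difference in mean change from baseline. It gives each subject's log baseline a coefficient of exactly 1, whatever its actual relation to the post-dose titer. If baseline predicts little, subtracting it adds noise. If it predicts partially, subtracting all of it over-corrects. A regression coefficient estimated from the data avoids both. Leaving out age and risk condition, which may also be prognostic, forgoes a further gain.

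What is at stake is precision. Section 8.3 says of Phase 2: "This is an estimation segment pertaining to immunogenicity and safety". With no hypotheses, interval width is much of what that segment delivers, and its Week 6 immunogenicity results feed the dose choice.

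**Working it through.** **Stated figure.** The protocol gives no sample-size target, SD, correlation or precision goal for these comparisons, so there is nothing to reproduce. Planned 95% half-widths, in SDs of log fold-rise, are t × sqrt(1/n1 + 1/n2):

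- 1.0 mg vs 2.0 mg, 150 vs 150: 0.227
- active vs matched placebo, 150 vs 50: 0.322
- Phase 3 subset of 102 + 102 = 204 subjects, about 136 vs 68 at 2:1: about 0.29

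**Baseline adjustment with a common slope.** Let s be the post-dose SD on the log scale, r = baseline SD / post-dose SD, and rho their correlation. Both r and rho are assumptions.

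- Variance of fold-rise: s²(1 + r² − 2·rho·r)
- Variance after ANCOVA: s²(1 − rho²)
- Excess carried by the fold-rise: s²(r − rho)², which is zero when r = rho
- Width ratio, ANCOVA / fold-rise: sqrt[(1 − rho²)/(1 + r² − 2·rho·r)]

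| r | rho = 0 | rho = 0.3 | rho = 0.5 | rho = 0.7 |
|---|---|---|---|---|
| 1.0 | 0.707 | 0.806 | 0.866 | 0.922 |
| 0.75 | 0.800 | 0.904 | 0.961 | 0.998 |
| 0.5 | 0.894 | 0.979 | 1.000 | 0.963 |
| 0.25 | 0.970 | 0.999 | 0.961 | 0.846 |

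Across the table the narrowing runs from 0 to about 29% (1 − 0.707). At r = 1 and rho = 0.5 the dose-comparison half-width falls from 0.227 to 0.227 × 0.866 = 0.197. At r = rho it does not move.

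**Baselines at the assay floor.** Phase 2 excludes subjects positive by serology or RT-PCR at Screening (Section 4.2.1), so many baselines may be at the floor. A simulation of 150 vs 150 (assumed slope 0.3 and residual SD 1) gave width ratios of 1.00, 0.998, 0.98 and 0.93 with 100%, 95%, 80% and 50% of baselines at the floor.

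**Age.** With the 60/40 split of 18–50 vs 51 and older, and an assumed age difference of d within-group SDs, the width ratio is 1/sqrt(1 + 0.6 × 0.4 × d²). This is 0.995 at d = 0.2, 0.971 at d = 0.5 and 0.931 at d = 0.8.

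**Unequal allocation with different slopes.** Take 150 active vs 50 placebo, with assumed baseline SD 0.5, residual SDs 0.5 (active) and 0.25 (placebo), and slopes 0 (active) and 1 (placebo). With coefficient b on baseline, the variance of the treatment difference is [(0 − b)² × 0.25 + 0.25]/150 + [(1 − b)² × 0.25 + 0.0625]/50.

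- Fold-rise, b = 1: 0.5/150 + 0.0625/50 = 0.00458
- Common-slope ANCOVA, b = 0.75 × 0 + 0.25 × 1 = 0.25: 0.2656/150 + 0.2031/50 = 0.00583
- With a treatment-by-centred-baseline term: 0.25/150 + 0.0625/50 + (1 − 0)² × 0.25/200 = 0.00417

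The SE ratios to the fold-rise are sqrt(0.00583/0.00458) = 1.13 and sqrt(0.00417/0.00458) = 0.95. Common-slope ANCOVA loses here, and the interaction term restores the advantage. At 136 vs 68 the same inputs give 0.00460 for both the fold-rise and common-slope ANCOVA (ratio 1.00).

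**By age group.** At 3:3:1:1, the 240/120/40 targets give about 90, 45 and 15 subjects per active arm. The dose-comparison half-widths are then about 0.29, 0.42 and 0.75 SD.

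**The case against.** The strongest reply is that nothing here is wrong. Fold-rise ratios with t-based intervals are a valid analysis, no test or sample size depends on them, and the gain is unknown and may be nil. That stands: this is a point about precision only.

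Several stronger readings are tempting, and the protocol does not support them.

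- A reader might infer that baseline is not adjusted for at all. It is: a fold-rise subtracts log baseline, and the summaries are stratified by NP status in Phase 2 and by baseline serostatus in the Phase 3 secondary analysis.
- A reader might infer that the intervals are certainly too wide. Without r, rho or an age effect, that cannot be shown.
- A reader might infer that ANCOVA can never be less precise. With a common slope, unequal allocation and different slopes it can be, as the 150 vs 50 example shows. The 150 vs 150 dose comparison is not exposed to this.
- A reader might extend the point to ELISpot. The width formula does not cover differences in medians. Median regression has no demonstrated gain and would change the quantity estimated.
- A reader might infer that these intervals decide the dose. Section 1.3.7 weighs safety, immunogenicity and practicality, and sets no interval-based rule.

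The per-protocol population and the split by disease status, which arises after randomization, also weaken any appeal to randomization. They weaken it equally for both analyses.

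**Conclusion.** The point holds for the titer endpoints as a low-cost refinement. The planned intervals are valid but may be wider than necessary. The narrowing from baseline adjustment is 0 to about 29% over the assumed values tabulated, and near zero for Phase 2 neutralizing titers if baselines sit at the floor. It could be larger among Phase 3 seropositive subjects, whose titers can vary within the stratum, but the protocol gives nothing to size this. Age adds roughly 0.5 to 7% under assumed differences of 0.2 to 0.8 SD.

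Separately, Section 8.5.1 does not provide Phase 2 results by age group, although Section 1.3.7 makes the dose decision at that level.

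**What to change.** In Sections 8.5.1, 8.5.2.2 and 8.5.9.2, for neutralizing-antibody and ELISA titers:

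1. Analyse log10 post-dose titer by ANCOVA with treatment, log10 baseline titer and age group, adding the risk-condition stratum in Phase 3. Report the adjusted GMT ratio with its 95% CI. With log baseline in the model, the treatment coefficient is the same whether the outcome is log post-dose titer or log fold-rise, so the quantity reported stays comparable.
2. For active vs placebo (3:1 within dose group in Phase 2, 2:1 in Phase 3), add a treatment-by-centred-baseline term with robust standard errors that allow for the baseline mean being estimated. Large-sample precision is then no worse than for the fold-rise.
3. Keep the stratification by NP status, disease status and serostatus, and keep the unadjusted fold-rise ratios as supportive.
4. Report Phase 2 results by age group, with the grouping stated in advance.
5. Leave the ELISpot difference in medians as planned.

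The cost is wording in three subsections and some programming. No new subjects, samples or data are needed.
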